### **4.3 Describe how the agent will be requested and provide mailing address and phone number.**

Ordered in Radiology Information System (RIS).

### **4.4 Agent Accountability**

RIS is password protected and part of the electronic medical records.

## **5. IMAGING SPECIFICS**

### **5.1 Modality or Modalities to be used**

PET/MRI

### **5.2 Details of Imaging (ie, dynamic, static, number of scans, etc.)**

A localizer MRI scan will be performed at 45 minutes after injection of 150 to 250 MBq of Ga-NeoBOMB1 (or Ga-PSMA R2, depending on randomization) to define the table positions. After correct positioning of the spatial acquisition windows is ensured, the combined PET/MRI acquisition will be initiated with 3–5 table positions at a 4-min acquisition time per table position. A volumetric T1 acquisition with fat-water separation and motion correction to enable free-breathing will be obtained at each table position and used for the generation of attenuation maps and for anatomic allocation of the PET results. Simultaneously with the start of the T1 MRI sequence, the PET acquisition will start at the same table position, thus ensuring optimal temporal and regional correspondence between MRI and PET data. The PET acquisition time will be 4 min per table position, taking delayed acquisition times and radioactive decay into account. As the T1 will take less than 4\ minutes, a rapid diffusion weighted MRI will also be performed. After completion of the PET acquisition, the table will be moved to the next table position and the procedure will be repeated. Upon completion of the PET acquisition for all stations, volumetric post-contrast T1- and T2-weighted MR images may be obtained at multiple stations as needed.

A localizer MRI scan will be performed at 45 minutes after injection of 150 – 250 MBq of Ga-PSMA R2 (or Ga-NeoBOMB1, depending on randomization) to define the table positions. After correct positioning of the spatial acquisition windows is ensured, the combined PET/MRI acquisition will be initiated with 3–5 table positions at a 4-min acquisition time per table position. ----Only MR sequences required for attenuation correction of PET data will be acquired.

Participants will be randomized to have Ga-NeoBOMB1 first followed by Ga-PSMA R2 within 2 weeks or Ga-PSMA R2 first followed by Ga-NeoBOMB1 within 2 weeks (50/50 chance for each schedule).

### **5.3 Details of image analysis**

The PET/MRI scans will be interpreted by ABNM certified Nuclear Medicine physicians and an ABR certified Radiologists. Drs [name], [name], [name], and [name] have significant clinical experience and will be blinded to the participants' medical history and the results of other imaging modalities. Consensus read will be obtained for each scan. Each lesion will be tabulated and a comparison of lesion detection by each scanner will be conducted.

The study team will communicate the results of the scans to the referring (treating) physicians who can decide what to do with the findings, including making treatment decisions.

## **6. STUDY PROCEDURES**

### **6.1. Pre-Study**

Potential subjects will be referred by treating physicians for participation in this imaging study. The following procedures will occur pre-study:

- Review of eligibility criteria
- Obtain informed consent
- Collect demographics
- Review medical history, including any concomitant medication. Record past prostate cancer diagnosis and treatment details.

### **6.2. Imaging Days**

Subjects will undergo two separate clinic visits for imaging. On each imaging day, subjects will receive an intravenous (IV) injection of investigational imaging agent (Ga-NeoBOMB1 or Ga-PSMA-R2) and undergo PET/MRI image collection as described in Section 2.5.

### **6.3. Follow-up**

Active subject participation ends after the 24 to 72 hour post-scan Safety Follow-up. Investigators will follow subjects by chart review for 12 months post-scan to record any standard of care biopsies or imaging results. If required by treating physicians for standard of care biopsies, the investigators will assist with identification of lesions that can be biopsied, based on Ga-NeoBOMB1 and/or Ga-PSMA-R2 PET/MRI findings.

If a subject transfers clinical care outside of Stanford Healthcare during the chart review clinical follow-up period, investigators will request permission to contact the treating physician to review medical records.

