## **10. MEASUREMENTS**

### **10.1 Primary outcome measure**

The principal goal of this study is to compare the diagnostic performance of Ga-NeoBOMB1 PET/MRI and Ga-PSMA R2 PET/MRI to that of MR alone in clinically (PSA) recurrent but CT-negative prostate cancer patients. The gold standard will be based on either biopsy or one-year follow-up with imaging.

Specifically, it is expected that:

1. At least 30% of these patients will have one or more lesions detected on Ga-NeoBOMB1 PET/MRI or Ga-PSMA R2 PET/MRI.
2. The proportion of patients with detected lesions will be higher for Ga-NeoBOMB1 PET/MRI or Ga-PSMA R2 PET/MRI than for MR alone.
  - Primary Outcome measure: Number of lesions detected by investigational imaging agent
  - Timeframe: Within 30 days
  - Description: The number of lesions detected on Ga- NeoBOMB1 PET/MRI, Ga-PSMA R2 PET/MRI, and conventional MR will be compared. Outcome will be reported as number of lesions detected per patient for each imaging method.

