#### **11.4 Key variables**

Reference standard: disease status of a lesion will be defined by biopsy of suspicious lesions, when clinically feasible. 12-months clinical follow-up with imaging will be gold standard if biopsy cannot be done.

Test to be evaluated:  $^{68}\text{Ga}$ -NeoBOMB1 and  $^{68}\text{Ga}$ -PSMA R2 positivity will be determined by the operator as uptake more than the adjacent background (malignant) or less (benign). Visual conspicuity against background on the diffusion weighted images and presence of an anatomically corresponding abnormality on the T1w and T2w images are the criteria for detecting a lesion on MRI.

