##### **11.4.1 Analysis Population**

All lesions identified by  $^{68}\text{Ga}$ -NeoBOMB1 PET/MRI and  $^{68}\text{Ga}$ -PSMA R2 PET/MRI.

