##### **11.4.2 Analysis Plan**

- Sensitivity, specificity, and positive and negative predictive value of imaging modalities will be estimated.
- Sensitivity and specificity of PET/MRI and MR alone will be compared by McNemar tests of paired proportions.
- The number and type of discrepancies between  $^{68}\text{Ga}$ -NeoBOMB1 and  $^{68}\text{Ga}$ -PSMA R2 will be tabulated.
- We will explore hypotheses about the reasons for such discrepancies, such as PSA level/velocity, Gleason score, and location.

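### Section 6.3 names only tracer PET/MRI findings as the basis for help with biopsy targets, and no section blinds lesion status, leaving the PET/MRI-versus-MR comparison open to differential-verification and review bias

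*Combined protocol and SAP*

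**What the plan says.** Section 6.3 has investigators follow participants by chart review for 12 months to record standard-of-care biopsies and imaging. It adds: "If required by treating physicians for standard of care biopsies, the investigators will assist with identification of lesions that can be biopsied, based on" NeoBOMB1 and/or PSMA-R2 PET/MRI findings. No other basis is named. Under 5.3, "The study team will communicate the results of the scans to the referring (treating) physicians who can decide what to do with the findings".

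On the reference standard, 11.4 says "disease status of a lesion will be defined by biopsy of suspicious lesions, when clinically feasible", and then "12-months clinical follow-up with imaging will be gold standard if biopsy cannot be done". Section 10.1 gives the same mixed standard for the principal goal, which is to compare each tracer PET/MRI with MR alone.

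The test is in 11.4.2: "Sensitivity and specificity of PET/MRI and MR alone will be compared by McNemar tests of paired proportions". The analysis population in 11.4.1 is "All lesions identified by" the two tracer PET/MRI scans.

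Sections 5.3 and 10.2 blind the scan reads. Nothing in 6.3, 10.4 or 11.4 says who assigns final lesion status or whether that person is blind to the scans. No analysis is split by type of reference standard.

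**The concern.** Two methods are compared on the same lesions, but only one of them has a stated route to biopsy. A lesion with tracer uptake can be pointed out to the physician planning a biopsy. A lesion seen only on the separate MR-alone read has no such route, and depends on whatever imaging the chart contains a year later. If that imaging misses some true disease, a malignant MR-only lesion is less likely to be confirmed than a malignant PET-only lesion. Confirmed discordant lesions then collect on the PET side of the McNemar table, even if the methods are equally sensitive.

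Review bias is a second route. Whoever reads the chart may know what the tracer scans showed, and the plan does not prevent that knowledge from colouring a doubtful status call. At stake is the sensitivity and specificity comparison that serves the principal goal.

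**Working it through.** **The plan's own figure.** Section 11.5 states 90% power for 60% versus 40% sensitivity, N = 50, one-sided 5%. It does not state the discordance. With 22% PET-only and 2% MR-only lesions the exact McNemar power is 90.2%. With independent readings (36% and 16%) it is 56.6%. So 90% is reachable only if MR finds almost nothing that PET misses. This is context: it neither supports nor weakens the point about verification.

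**Inputs from the plan.** One-sided 5% level and about 1/3 biopsied (11.5); biopsy first, 12-month imaging second (11.4).

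**Assumptions, not in the plan.** The 1/3 is read as the biopsied share of PET-positive lesions, although 11.5 words it for patients. No PET-negative lesion is biopsied. Biopsy is perfect. Follow-up imaging confirms a true lesion with probability f. There are 50 malignant lesions, each method is 50% sensitive, readings are independent (25% both, 25% PET-only, 25% MR-only, 25% neither), and MR-only lesions are in the analysis set.

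**Confirmation probabilities.** PET-positive: c = 1/3 + (2/3)f. All others: f.

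**False rejection.** P(PET-only and confirmed) = 0.25c; P(MR-only and confirmed) = 0.25f. The discordant count D is binomial(50, 0.25c + 0.25f). Given D, the PET-only count is binomial(D, c/(c + f)). The test rejects when the upper tail under one half is at most 0.05.

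**Apparent gap in sensitivity.** 0.25(c − f) / (0.5c + 0.5f).

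| f | c | Expected PET-only : MR-only confirmed | Rejection | Apparent gap (true gap 0) |
|---|---|---|---|---|
| 1.0 | 1.000 | 12.5 : 12.5 | 3.4% | 0 points |
| 0.8 | 0.867 | 10.8 : 10.0 | 4.8% | 2.0 points |
| 0.5 | 0.667 | 8.3 : 6.25 | 8.9% | 7.1 points |
| 0.2 | 0.467 | 5.8 : 2.5 | 18.5% | 20.0 points |

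The first row is below 5% because the exact test is conservative.

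**At the plan's expected sensitivities (60% and 40%, independent readings).** Apparent gap = (0.36c − 0.16f) / (0.6c + 0.4f). At f = 0.8: (0.312 − 0.128)/0.84 = 21.9 points. At f = 0.5: (0.240 − 0.080)/0.60 = 26.7 points. The true gap is 20 points.

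**Direction.** Suppose there are m MR-only false positives per true lesion and follow-up wrongly confirms each with probability g. Then gm is added to the MR-only cell and to the denominator.
- True 60% and 40%, f = 0.8, g = 0.5, m = 0.3: (0.312 − 0.128 − 0.150)/(0.84 + 0.15) = 3.4 points, against 20 true.
- True 50% and 50%, f = 0.8, g = 0.5, m = 0.1: (0.2167 − 0.2000 − 0.0500)/(0.8333 + 0.0500) = −3.8 points. The tilt has reversed.

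**Link with 11.4.1.** If only PET-identified lesions are analysed, the MR-only cell is empty and their verification has no effect on the McNemar table. PET sensitivity is then 100% by construction. In the equal-sensitivity case MR shows 0.25c/0.50c = 50%, an artificial gap of 50 points. That is a larger source of bias than 6.3.

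**The case against.** The strongest reply is that 6.3 describes modest, conditional help. It is triggered by the treating physician, who decides what to do. Using a new scan to locate lesions in men whose conventional imaging was non-contributory is a normal constraint. The scan has an MR component, so some MR-visible lesions may be pointed out too. The labelled primary outcome, lesions detected per patient, needs no reference standard. All of this stands. It limits the size, but it does not give the MR-alone read a stated place in 6.3 or blind the status call. Section 11.4 also defines tracer positivity by uptake, and 10.2 has MR evaluated blind to PET.

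Three stronger readings are tempting, and the documents do not support them.

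- A reader might infer that 6.3 fixes the direction towards PET. It does not: false confirmation of MR-only lesions can reverse it, as shown. More biopsy of PET lesions can also expose PET false positives, which counts against PET on specificity and predictive value.
- A reader might assume 90% confirmation for PET-positive and 45% for MR-only lesions and report 31% false rejection. With one third biopsied, 90% implies f = (0.90 − 0.333)/0.667 = 0.85, so MR-only confirmation is 85% and the test rejects 4.4% of the time. Even f = 0.45 gives 9.9%.
- A reader might infer that the investigators who assign status are known to be unblinded. The text says only that investigators review charts; blinding is not specified.

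**Conclusion.** The point holds as a gap in the plan. The tests under evaluation are the only named input to help with biopsy targets, biopsy is the preferred reference, and neither a blinded status call nor an analysis by verification route offsets this. Under the stated assumptions the effect is nil if follow-up imaging is as good as biopsy, small at f = 0.8, and material at f = 0.5 or below. Section 2.1 cites sensitivities of 30–80% for CT or MRI in nodes and 25–54% for ultrasound or contrast-enhanced CT in local recurrence. Those are single-examination figures, but they make f below 1 plausible. The calculation covers the biopsy route only; review bias is not quantified and could add to it. The direction is likely, not certain, and MR-only lesions matter here only if 11.4.1 admits them. The change should be made because it is cheap and protects the comparison behind the principal goal.

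**What to change.** 1. **Section 6.3.** When a treating physician asks for help, have the investigators report suspicious lesions from the MR-alone read as well as from both tracer reads. Do not mask the source: 5.3 already sends scan results to that physician, so masking would fail, and it would intrude on clinical management. All biopsy decisions stay with the treating physician.
2. **Section 11.4.** Have 12-month lesion status assigned from biopsy and follow-up records by an existing team member who is blind to which method detected the lesion, with index-scan results removed from the packet. Because 5.3 calls for a consensus read of each scan, check that someone who did not read that participant's scans is available.
3. **Section 11.4.2.** Tabulate verification route (biopsy, follow-up imaging, unverified) by index result, and repeat the sensitivity comparison by route.
4. **Section 11.4.1.** Reconcile the population with the MR-alone comparison at the same time by stating whether MR-only lesions are included. Without that, step 1 cannot benefit the McNemar test.

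The cost is protocol wording, a lesion list and a redacted record packet. No additional biopsies are required. The small downside is that MR reads must be finished before a biopsy request is answered. Steps 2 and 3 remain useful even if biopsies have already begun.

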### **6.4. Criteria for Removal from Study**

The Protocol Director may withdraw subjects from the study for one or more of the following reasons: failure to follow the instructions of the Protocol Director and/or study staff;

determination that continuing the participation could be harmful to the subject; the study is cancelled or other administrative reasons.

## 6.5. Alternatives

The alternative is to not participate in the study.

## 7. STUDY CALENDAR

	Pre-Study	Scan Date	24 - 72 Hours Post-Scan	12 Months
Informed consent	X			
Demographics	X			
Medical history	X			
 Ga-NeoBOMB1		X a		
 Ga-PSMA R2 (within 2 weeks)		X a		
Follow-up Call to Participant			X	
Chart review b				X

a: Subjects will undergo either Ga-NeoBOMB1 PET/MRI followed within 2 weeks by Ga-PSMA-R2 PET/MRI, or Ga-PSMA-R2 PET/MRI followed within 2 weeks by Ga-NeoBOMB1 PET/MRI

b: Subjects will be followed by chart review for 12 months from initial scan date. If a subject transfers clinical care from Stanford Healthcare, investigators may request records from the treating physician.

## 8. ADVERSE EVENTS AND REPORTING PROCEDURES

### 8.1 Potential Adverse Events

The administration of the radioactive substance will feel like a slight pinprick when given by IV injection. Patients who are claustrophobic may feel some anxiety while positioned in the scanner. Also, some patients find it uncomfortable to hold one position for more than a few minutes. Because the radioactivity is very short-lived, the expected radiation exposure of the whole body and critical organs is low. The substance amount (PSMA R2 and NeoBOMB1) is so small that it does not affect the physiological processes of the body.

This research study involves exposure to radiation from one Ga-NeoBOMB1 PET/MRI. There is no radiation exposure from MRI. The estimated effective dose for total human body, for an injected dose of 150 to 250 MBq is between 5.85 to 9.75 mSv, approximately equal to 11.7 to 19.5% of the limit that radiation workers (for example, a hospital X-ray technician) can receive in one year.

This research study also involves exposure to radiation from one Ga-PSMA-R2 PET/MRI. There is no radiation exposure from MRI. The effective dose from Ga-PSMA-R2 PET is similar to Ga-PSMA-11 or Ga-PSMA-617. The estimated effective dose for total human body, for an injected dose of 150 to 250 MBq, is between 3.15 to 5.25 mSv, approximately equal to 6.3-10.5% of the limit that radiation workers (for example, a hospital X-ray technician) can receive in one year.

## **8.2 Adverse Event Reporting**

We do not anticipate hazardous situations for the subjects because of this protocol. However, procedures will be in place for verification of correct radiopharmaceutical dose and route of administration (ie, each dose will be double checked for dosimetry and quality by a researcher and technologist). The study Principal Investigator (PI) or his designee will report unexpected AEs related to the Stanford CCTO Safety Coordinator within 10 working days of becoming aware of the event (5 days if the event is life-threatening or resulted in death) using the Adverse Events Communication Form. If the principal investigator determines the unanticipated adverse effect presents an unreasonable risk to subjects, the study will be terminated as soon as possible, but no later than 5 working days after the PI makes the determination and no later than 15 working days after first receiving notification of the effect.

## **9. REGULATORY CONSIDERATIONS**

### **9.1 Institutional Review of Protocol**

The protocol, the proposed informed consent and all forms of participant information related to the study (eg, advertisements used to recruit participants) will be reviewed and approved by the Stanford IRB. Any changes made to the protocol will be submitted as a modification and will be approved by the IRB prior to implementation. The Protocol Director will disseminate the protocol amendment information to all participating investigators.

### **9.2 Data Management Plan**

The CRFs will be stored in a locked office in the Nuclear Medicine clinic. Records will be kept using OnCore.

During the clinical investigation, the Protocol Director will evaluate the progress of the trial, including periodic assessments of data quality and timeliness, participant recruitment, accrual and retention, participant risk versus benefit, performance of trial sites, and other factors that can affect study outcome. Monitoring of the trial will occur every 8 weeks and a record of monitoring activities will be maintained by the study team.

The Stanford Cancer Institute Data and Safety Monitoring Committee (DSMC) will audit study related activities to determine whether the study has been conducted in accordance with the protocol, local standard operating procedures, FDA regulations, and Good Clinical Practice (GCP). This may include review of regulatory binders, case report forms, eligibility checklists, and source documents. In addition, the DSMC will regularly review serious adverse events and protocol deviations associated with the research to ensure the protection of human subjects. Results of DSMC audits will be communicated to the IRB and the appropriate regulatory authorities at the time of continuing review, or in an expedited fashion, as needed.

## **10. MEASUREMENTS**

### **10.1 Primary outcome measure**

The principal goal of this study is to compare the diagnostic performance of Ga-NeoBOMB1 PET/MRI and Ga-PSMA R2 PET/MRI to that of MR alone in clinically (PSA) recurrent but CT-negative prostate cancer patients. The gold standard will be based on either biopsy or one-year follow-up with imaging.

Specifically, it is expected that:

1. At least 30% of these patients will have one or more lesions detected on Ga-NeoBOMB1 PET/MRI or Ga-PSMA R2 PET/MRI.
2. The proportion of patients with detected lesions will be higher for Ga-NeoBOMB1 PET/MRI or Ga-PSMA R2 PET/MRI than for MR alone.
  - Primary Outcome measure: Number of lesions detected by investigational imaging agent
  - Timeframe: Within 30 days
  - Description: The number of lesions detected on Ga- NeoBOMB1 PET/MRI, Ga-PSMA R2 PET/MRI, and conventional MR will be compared. Outcome will be reported as number of lesions detected per patient for each imaging method.

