#### **11.5 Sample size justification**

The following estimate is for a per-lesion analysis. We expect approximately 70% of patients (~35) to have one or more PET-positive findings and approximately 1/3 to be biopsied. Our existing data for  $^{68}\text{Ga}$  PSMA-11 and  $^{68}\text{Ga}$ -RM2 (please see attached publications) indicate no false positive findings based on biopsy. We cannot predict an average number of lesions per patient given small data available to date, but if only half of the positive patients have more than one lesion, this will easily yield 50 lesions. We also expect the sensitivity of MR alone to be roughly 40%, while that of PET to be roughly 60% or more. A sample size of 50 patients will provide 90% power at one-sided 5% error to detect such a difference. Participants who complete only one PET/MRI scan (either due to withdrawal of consent or loss to follow-up) will not be replaced with additional subjects.

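### The lesion count labelled primary in 10.1 is not what the 90% power covers, not what 10.1 expects, and not what 11.4.2 tests

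*Combined protocol and SAP*

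**What the plan says.** Section 10.1 contains three different targets.

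- **Goal.** "The principal goal of this study is to compare the diagnostic performance of" each PET/MRI with that of MR alone, judged against biopsy or one-year follow-up imaging.
- **Expectations.** The first reads "At least 30% of these patients will have one or more lesions detected on" one or the other PET/MRI. The second reads "The proportion of patients with detected lesions will be higher for" one or the other PET/MRI than for MR alone. Both are about patients, not lesions.
- **Labelled primary outcome.** "Primary Outcome measure: Number of lesions detected by investigational imaging agent", with "Timeframe: Within 30 days" and "Outcome will be reported as number of lesions detected per patient for each imaging method". The counts are to be compared across the three methods, but no test and no target difference are given.

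The only inferential analysis in section 11.4.2 is "Sensitivity and specificity of PET/MRI and MR alone will be compared by McNemar tests of paired proportions". The other items there are accuracy estimates, a table of discrepancies between the two tracers, and exploration of their causes.

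Section 11.5 says "The following estimate is for a per-lesion analysis". It assumes sensitivity of about 40% for MR and 60% or more for PET, and states 90% power at one-sided 5% with 50 patients. It also says that the mean number of lesions per patient cannot be predicted.

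Under section 11.4, positivity is the operator's judgement of uptake against adjacent background, and the reference standard is biopsy or 12-month imaging. Verification enters through the accuracy analyses in 11.4.2 and the secondary outcome in 10.4, the share of detected lesions confirmed malignant.

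**The concern.** If the plan is followed literally, the outcome called primary is reported without a test, and the test that was powered is not on the primary outcome. Three quantities (lesion count, patient proportion, per-lesion sensitivity) could each be presented afterwards as the main result, and nothing in the plan settles which one decides.

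The count also has no reference standard. Its 30-day window closes before the 12-month standard is available, so every false-positive focus adds to it in the same way as a true lesion. A tracer could look better than MR by over-calling.

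**Working it through.** **1. Targets side by side**

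| Quantity | Unit | Verified? | Test named | Power stated |
|---|---|---|---|---|
| Labelled primary outcome (10.1) | lesions per patient | no | none | none |
| Expectations (10.1) | patients with at least one lesion | no | none | none |
| Sensitivity, specificity (11.4.2, 11.5) | lesion | yes | McNemar | 90%, for sensitivity |

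No row has the primary label, a test and a power figure together.

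**2. The plan's 90%**

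Inputs from 11.5: 40% against 60%, 50 lesions, one-sided 5%. The lesion number is consistent with its scenario: if half of about 35 positive patients have two lesions and half have one, the total is 17.5 × 1 + 17.5 × 2 = 52.5.

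- One-sample normal approximation against a fixed 40%: SE = √(0.6 × 0.4 / 50) = 0.0693. Power = Φ(0.20/0.0693 − 1.645) = Φ(1.24) = 89.3%.
- Exact McNemar, the test in 11.4.2. Let D be the share of discordant lesions, with p10 = (D + 0.20)/2 and p01 = (D − 0.20)/2. Sum over the number k of discordant lesions: Bin(k; 50, D) × P(Bin(k, p10/D) ≥ c_k), where c_k is the smallest count with P(Bin(k, ½) ≥ c_k) ≤ 0.05.

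| D | 0.20 (minimum) | 0.24 | 0.30 | 0.40 | 0.52 (independent reads) |
|---|---|---|---|---|---|
| Power | 98.2% | 90.2% | 80.7% | 67.9% | 56.6% |

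For independent reads, D = 0.6 × 0.6 + 0.4 × 0.4 = 0.52. The plan gives no discordance rate. These figures treat lesions as independent of one another.

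**3. Power for the lesion count**

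This cannot be computed, because no mean, SD or target difference is given. As a range of assumptions (paired normal approximation, n = 50, one-sided 5%, 90% power), the detectable mean difference is (1.645 + 1.282) × SD/√50 = 0.414 × SD. That is 0.21, 0.41, 0.62 or 0.83 lesions per patient for SDs of 0.5, 1.0, 1.5 or 2.0.

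**4. Power for the patient proportion**

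The PET-positive rate is taken as 70% from 11.5, which does not tie it to one tracer. The MR patient rate m is not in the documents and is assumed. Exact McNemar, n = 50, one-sided 5%. Independent reads: p10 = 0.70(1 − m), p01 = 0.30m. Nested (every MR-positive patient also PET-positive): p10 = 0.70 − m, p01 = 0.

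| m | Independent p10, p01 | Power | Nested p10 | Power |
|---|---|---|---|---|
| 28% | 0.504, 0.084 | 99.4% | 0.42 | >99.9% |
| 40% | 0.420, 0.120 | 88.8% | 0.30 | >99.9% |
| 50% | 0.350, 0.150 | 58.1% | 0.20 | 98.2% |

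**5. Effect of false positives (assumed rates)**

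- Count: a tracer with MR's 40% sensitivity and f false foci per true lesion present, against MR with none, shows (0.40 + f)/0.40 times the MR count: 1.63 for f = 0.25 and 2.25 for f = 0.50.
- Ranking: with 50 true lesions, 60% sensitivity and no false positives counts 30. With 40% sensitivity and 15 false positives the count is 20 + 15 = 35, although only 20/35 = 57% are real.
- Patient proportion: suppose MR is positive in 40% of patients, and the tracer is positive in the same patients and falsely positive in 25% of the rest (0.25 × 0.60 = 0.15). Exact McNemar needs at least 5 discordant patients, since ½⁵ = 0.031. P(Bin(50, 0.15) ≥ 5) = 89%, so the tracer would usually be declared superior on false positives alone.

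**6. The 30% expectation**

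If the true rate is 30%, P(X ≥ 15 of 50) = 55%, so merely observing 30% shows little. P(X ≥ 21) = 4.8%. At a true 70%, P(X ≥ 21) exceeds 99.9%.

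**The case against.** The strongest reply is that this is a single-arm phase II imaging study whose lesion count is to be reported, and that over-calling would not stay hidden. Section 10.4 reports the share of detected lesions confirmed malignant, 11.4.2 estimates specificity and predictive values, and 5.3 foresees a comparison of lesion detection. Section 11.5 cites no false positives on biopsy. Moreover, on a common set of verified lesions, comparing sensitivities amounts to comparing verified counts, so the primary and the powered quantities are related.

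Much of this stands as mitigation. It does not give the labelled primary outcome a test or a power figure. The 10.4 outcome is secondary and arrives at one year. The biopsy evidence comes from two other tracers, and 11.5 expects only about one third to be biopsied here.

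Three stronger readings are tempting and should not be drawn.

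- **That the 90% is wrong.** It is reproducible, but for sensitivity, and with either a fixed 40% comparator or discordance of about 0.24.
- **That a patient-level endpoint would remove the false-positive problem.** It caps the gain at one per patient but is just as unverified, as step 5 shows.
- **That a few patients would dominate the count.** The documents give no lesion distribution. Two lesions in each multi-lesion patient, as in step 2, gives those patients 35/52.5 = 67% of lesions, and nothing supports a more extreme figure.

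Nor should the 58% be quoted alone. It needs both an MR rate of 50% and independent reads, and since both methods image the same disease, positive correlation is plausible.

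**Conclusion.** The mismatch is in the text and does not depend on any assumption. The unverified count is labelled primary, patient proportions are expected, and per-lesion sensitivity is tested and powered. The 90% does not belong to the primary outcome, and no listed test addresses the count or the patient proportion. False-positive calls inflate the count, with only partial correction from 10.4 and 11.4.2.

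The size depends on the endpoint chosen. For sensitivity on 50 lesions, exact McNemar power runs from 98% at the minimum discordance to 57% at independence. For the patient proportion it runs from 58% to above 99%, depending on an MR rate and a correlation that the documents do not give. For the count it cannot be stated. The false-positive figures illustrate a mechanism and do not predict these tracers' performance.

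**What to change.** Wording in 10.1, 11.4.2 and 11.5:

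1. **One confirmatory endpoint.** Name it in 10.1 and align 11.4.2 and 11.5 with it. Say in 11.5 that the 90% applies to per-lesion sensitivity on about 50 lesions, not to the lesion count, and that under exact McNemar it needs discordance of about 0.24 (81% at 0.30, 57% at 0.52).
2. **Patient-level test.** In 11.4.2, add an exact McNemar test on patients for the proportion with at least one detected lesion, PET/MRI against MR alone. Say whether the word or in 10.1 means either tracer or each tracer, and give a multiplicity rule if each. Give power over the range in step 4.
3. **All and verified lesions.** Report lesions per patient as a paired comparison. Show both the count and the patient proportion for all detected lesions and again for lesions verified by biopsy or 12-month imaging, so that over-calling cannot by itself produce a favourable primary result. The 30-day window can then apply only to the unverified version.
4. **The 30% expectation.** If it is kept as a test, use an exact binomial test with the cut-off set for the number actually scanned (at least 21 of 50, or 20 of 45), because 11.5 does not replace participants who complete only one scan.

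No new scans, patients or data are needed, since 12-month follow-up is already planned. The small downside is that the restated power may be below 90%.
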